Official Title: Fundus Finding and Thiol-Disulfide Homeostasis in Gestational Diabetes

ClinicalTrials.gov Identifier: NCT05958927

Document Date: April 13, 2023

Study Protocol

This is a prospective case-control study conducted in 26 pregnant patients diagnosed with impaired glucose status (gest DM, IGT, high 50 gr GTT level) at 24-28 weeks of pregnancy and 34 healthy pregnant women with normal glucose status in the Uşak Training and Research Hospital Gynecology and Ophthalmology clinic.

A total of 60 pregnant women participated in the study. (26 gestational diabetes and 34 healthy pregnant women). Investigators excluded patients with type 1 diabetes mellitus and type 2 diabetes mellitus, patient that history of ocular surface disease, topical/systemic medical therapy, with ocular inflamatuar disease such as üveitis. The patients who is healthy pregnant and gestasional diabetes mellitus pregnant were recruit to this study. Controls group included only healthy pregnant.

All patients underwent a comprehensive ophthalmologic examination that included best-corrected visual acuity, slit-lamp examination, dilated fundus examination and applanation tonometry. Optic nerve retinal nerve fiber thickness and macular thickness were measured with OCT device in all patients

Tears analysis is less invasive, safe and acceptable method for research. Tear samples, Schirmer paper strips were placed in the lower conjunctival fornix of the right eye for a maximum of 5 minutes. Care was taken not to use tear stimulation, topical anesthetic or other eye drops. Attention was paid to factors such as lighting and room temperature. The ocular surface was not damaged. Tear samples were collected by a single individual (SD). A 15-20 mm test result was considered as enough for biochemical analysis. Schirmer strips were diluted with 500 μ l previously cooled PBS (phosphate-buffered saline), and stored in Eppendorf tubes until analysis (-80°C).

At the end of the study, fundus findings and tear oxidative stress values of both groups will be compared. ELISA method will be used for determination of tear oxidative stress findings.

The study followed the tenets of the declaration of Helsinki and was approved by the Uşak üniversitesi Ethics Committee (13.04.2023 / 93-93-04). Written and informed con-sent of participants was obtained for each patient prior to the study.

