Official Title: Fundus Finding and Thiol-Disulfide Homeostasis in Gestational Diabetes

ClinicalTrials.gov Identifier: NCT05958927

Document Date: April 13, 2023

Statistical analysis

NCSS (Number Cruncher Statistical System) 2007 (Kaysville, Utah, USA) program will be used. While evaluating the study data, the distribution of the data will be evaluated with the Shapiro-Wilk Test, as well as the descriptive statistical methods (Mean, Standard Deviation, Median, Frequency, Ratio, Minimum, Maximum). Mann-Whitney U test will be used in comparisons of two groups that do not show normal distribution of quantitative data, and Student's t test will be used in case of normal distribution. Chi-square analysis will be used to determine the relationship between qualitative data. In order to determine the relationship between quantitative data, Pearson correlation analysis will be used in case of normal distribution and Spearman's correlation

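### The same 26 cases are defined both as mixed impaired glucose status and as gestational diabetes, so the two-group comparison may not support a gestational diabetes conclusion

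*Protocol*

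**What the plan says.** The Protocol describes the case group in three places.

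- **Paragraph 1:** the cases are "26 pregnant patients diagnosed with impaired glucose status (gest DM, IGT, high 50 gr GTT level) at 24-28 weeks of pregnancy", set against "34 healthy pregnant women with normal glucose status".
- **Paragraph 2, counts:** "A total of 60 pregnant women participated in the study", broken down as "26 gestational diabetes and 34 healthy pregnant women".
- **Paragraph 2, recruitment:** "The patients who is healthy pregnant and gestasional diabetes mellitus pregnant were recruit to this study". Impaired glucose tolerance and a raised 50 g test are not mentioned here.

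The title on both documents is "Fundus Finding and Thiol-Disulfide Homeostasis in Gestational Diabetes".

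On analysis, the Protocol says that "fundus findings and tear oxidative stress values of both groups will be compared". The SAP names generic two-group tests: "Mann-Whitney U test will be used in comparisons of two groups that do not show normal distribution of quantitative data", with Student's t test where the data are normal. Neither document, as far as its text goes, gives the number of cases in each glucose category, the criteria that assigned them, or an analysis by category. The SAP text stops mid-sentence at Spearman's correlation, so that absence is claimed only for the text available.

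**The concern.** In a case-control study the case definition fixes what the comparison estimates. Paragraph 1 lists gestational diabetes as one of three entries under a broader heading. A woman with only impaired glucose tolerance, or only a high 50 g result, is a case under paragraph 1. Under paragraph 2 she is neither a gestational diabetes case nor, given that controls have normal glucose status, a control.

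Followed as written, the study could report a contrast from a mixed group under a gestational diabetes label, and a reader could not tell. The consequence would depend on the women without gestational diabetes. If they also differ from controls, a positive result is not specific to gestational diabetes. If they differ little or not at all, the gestational diabetes effect is diluted and may be missed. No choice between the t test and the Mann-Whitney test repairs either problem.

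**Working it through.** **1. Are the two descriptions about the same women?** The stated total is 60, and 26 + 34 = 60. The group sizes are 26 and 34 in both paragraphs, so the same 26 women carry both descriptions.

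**2. Can both descriptions hold?** Only if all 26 have gestational diabetes. Paragraph 1 does not say so, and nothing states that its three terms are used as synonyms. That leaves two possibilities:

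- *All 26 have gestational diabetes.* Paragraph 1 is wrong, and there is no mixture and no dilution.
- *The 26 are a mixture.* Paragraph 2 and the title are wrong, and the comparison estimates impaired versus normal glucose status.

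The documents do not show which is true.

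**3. What could a mixture do? (Illustration only.)** From the documents: 26 cases and 34 controls. Assumed, because the documents give none of these: a gestational diabetes effect of d = 0.8 SD, equal SDs, two-sided 5% testing, and k of the 26 cases without gestational diabetes, each carrying a fraction r of d.

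Pooled mean difference = d × [(26 − k) + r·k] / 26.

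For k = 13:

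- r = 0: 0.8 × 13/26 = 0.40 SD
- r = 0.5: 0.8 × 19.5/26 = 0.60 SD
- r = 1: 0.80 SD

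Pooled power comes from simulated two-sample t tests (the mixture slightly raises the variance among cases). Power for gestational diabetes cases alone against the 34 controls comes from the noncentral t distribution.

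| k without GDM | Pooled, r = 0 | Pooled, r = 0.5 | Pooled, r = 1 | GDM only vs 34 controls |
|---|---|---|---|---|
| 0 | 86% | 86% | 86% | 86% (n = 26) |
| 6 | 62% | 76% | 86% | 80% (n = 20) |
| 9 | 48% | 70% | 86% | 75% (n = 17) |
| 13 | 30% | 61% | 86% | 67% (n = 13) |
| 17 | 17% | 52% | 86% | 55% (n = 9) |

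The pooled comparison becomes the more powerful one once r exceeds about 66%, 64%, 59% and 53% for k = 6, 9, 13 and 17. Restricting to gestational diabetes is therefore not a guaranteed gain in power.

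**4. Precision of a restricted comparison.** The 95% half-width in SD units is t(0.975, n + 32) × √(1/n + 1/34).

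- n = 26: 2.002 × 0.2605 = 0.52
- n = 20: 2.007 × 0.2818 = 0.57 (8% wider)
- n = 17: 2.010 × 0.2970 = 0.60 (14% wider)
- n = 13: 2.014 × 0.3261 = 0.66 (26% wider)
- n = 9: 2.020 × 0.3749 = 0.76 (45% wider)

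**The case against.** The strongest reply is that this is loose wording. Paragraph 2 may use gestational diabetes as shorthand for the group that paragraph 1 has already defined. The Protocol would then compare impaired with normal glucose status, as intended, and the sample, tests and main comparison would not change. The documents also state no hypothesis or estimand specific to gestational diabetes, so the claim at risk is inferred from the title and group labels. The incomplete SAP text might contain an analysis by category. Finally, the power figures rest entirely on assumed inputs.

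Part of this stands. The harm to the result is conditional on the group being mixed, and the power figures show only what a mixture could do. The shorthand reading does not remove the problem, however. It is the case in which paragraph 1 is right, and it leaves the title, the counts and the recruitment sentence naming a condition that some of the women may not have. The missing SAP text does not affect the contradiction, which lies wholly within the Protocol.

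**Conclusion.** The concern holds. The case definition contradicts itself, and this must be settled before the groups are compared, because the title and conclusion depend on it. Confidence is high for the contradiction; dilution is conditional on the group being mixed.

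The size of any effect cannot be derived from the documents. Under the assumed 0.8 SD effect and the splits tried, pooled power ranges from 17% to 86%, depending on how many women lack gestational diabetes and how far they differ from controls. The reason to separate the categories is to know what the result means, not an assured increase in power.

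**What to change.** 1. Reconcile the two Protocol paragraphs. Report how many of the 26 fall in each category (gestational diabetes, impaired glucose tolerance, high 50 g result only) and the test result that assigned each woman.
2. If all 26 have gestational diabetes, correct paragraph 1. Nothing else changes.
3. If the group is mixed, keep the pooled comparison as the main one, but call it impaired versus normal glucose status in the title, group labels and conclusion, and draw no claim specific to gestational diabetes from it. Where the category is recorded, add gestational diabetes versus healthy as a named supportive comparison, with an estimate and 95% interval. Making the restricted comparison the main one would also be defensible if it is chosen before the data are analysed.

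**Cost.** Steps 1 and 2 and the relabelling are wording. The documents do not say whether a category is recorded for each case, so the counts and the supportive comparison may need a records check. A woman who cannot be classified stays in the pooled comparison only. The price is a narrower claim from the pooled result and, for the supportive comparison, the wider interval shown in the working.

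### Only the cases are tied to 24-28 weeks; with no gestational window for controls or for the eye and tear measurements, pregnancy stage can enter every group comparison

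*Protocol*

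**What the plan says.** The opening paragraph of the Protocol describes the 26 cases and then the controls in one phrase: "diagnosed with impaired glucose status (gest DM, IGT, high 50 gr GTT level) at 24-28 weeks of pregnancy and 34 healthy pregnant women". Its full description of the control group is "34 healthy pregnant women with normal glucose status". The next paragraph adds "Controls group included only healthy pregnant". The only statement on recruitment is "The patients who is healthy pregnant and gestasional diabetes mellitus pregnant were recruit to this study".

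The gestational weeks thus qualify the diagnosis in the cases. For controls, the Protocol names no week of pregnancy, no glucose test, no source visit and no matching.

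On measurement, the Protocol says "All patients underwent a comprehensive ophthalmologic examination", with OCT for everyone and a tear strip from the right eye. It gives no gestational age for these measurements in either group and no interval from glucose test to examination. It then plans a direct comparison of fundus findings and tear oxidative stress between the groups.

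The Statistical analysis section of the SAP lists Student's t, Mann-Whitney, chi-square and correlation analyses. The text available has no covariate adjustment, stratification or matching. It breaks off in the sentence on correlation, so it cannot be known whether anything followed.

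**The concern.** In a case-control comparison, controls should come from the population and time point that produced the cases. Here the cases come from a test in a defined part of pregnancy, and nothing written places the controls there too.

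If an OCT thickness or a tear oxidative stress marker changes with pregnancy stage, and the groups were measured at different average weeks, the unadjusted difference combines the glucose effect with a stage effect. This would affect every outcome, and the listed tests cannot separate the two. If the groups' weeks did not overlap at all, adjustment would only extrapolate. That is why the window belongs in the control definition as well as in the analysis.

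**Working it through.** **Text check.**

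| Item | Cases (26) | Controls (34) |
|---|---|---|
| Glucose status | impaired | normal |
| Named glucose test | partly (50 g test named) | none |
| Week of glucose assessment | 24-28 | not given |
| Week of OCT and tear strip | not given | not given |
| Interval from test to examination | not given | not given |
| Adjustment for pregnancy stage in the SAP text available | none | none |

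The asymmetry is in the third row. The next two rows show that even for cases the window dates the diagnosis and leaves the eye and tear measurements undated.

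**No planned figure to reproduce.** The documents give no sample-size calculation, alpha, power, effect size or SD. The group sizes agree with the stated total: 26 + 34 = 60. What follows illustrates scale only.

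**Assumptions.** Two-sided alpha 0.05, equal SDs, Student's t with 26 + 34 - 2 = 58 df, and outcomes in SD units. The shift is a between-group difference caused only by pregnancy stage.

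**Standard error.** SE = sqrt(1/26 + 1/34) = 0.2605 SD.

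**False-positive rate with no glucose effect.** The noncentrality is shift / SE, and the rejection rate comes from the noncentral t.

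- Shift 0.05 SD: 0.05 / 0.2605 = 0.19, giving 5.4%.
- Shift 0.20 SD: 0.20 / 0.2605 = 0.77, giving 11.7%. The normal approximation gives 12.0%.

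A 0.20 SD shift would arise, for example, from an assumed drift of 0.05 SD per week and a 4-week difference in mean gestational age (0.05 x 4 = 0.20). The documents give neither quantity.

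**Power if the shift opposes a true effect.** The reference effect is 0.742 SD. It is simply the difference with 80.0% power at 26 v 34 and is not a planned effect.

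- Shift 0.05 SD: 0.742 - 0.05 = 0.692 SD, power 74.3%.
- Shift 0.20 SD: 0.742 - 0.20 = 0.542 SD, power 53.4%.

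**Cost of restricting the controls.** SE = sqrt(1/26 + 1/n), power at 0.742 SD, noncentral t with 24 + n df.

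| Controls kept (n) | SE (SD) | Power |
|---|---|---|
| 34 | 0.26 | 80% |
| 28 | 0.27 | 76% |
| 24 | 0.28 | 73% |
| 17 | 0.31 | 64% |

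**The case against.** The strongest defence is that normal glucose status, set directly against cases defined by glucose testing, most naturally means controls who passed the same routine screen. On that reading the groups share a window, and only a sentence is missing. Nothing in the documents shows that the groups differed in gestational age when measured, every shift used above is assumed, and ordinary adjustment would handle a stage difference if the weeks overlap.

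Much of this stands. A shared screen is plausible, and neither the existence nor the direction of a bias is established. But a shared screen would fix only the week of testing. The week of OCT and tear sampling would remain open in both groups, and the SAP text available contains no adjustment.

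A reader might infer two stronger criticisms, which the documents do not support:

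- **Controls recruited through the eye clinic, and so selected on the outcome.** The phrase "in the Uşak Training and Research Hospital Gynecology and Ophthalmology clinic" gives the setting of the whole study. Slit-lamp examination, tonometry and OCT in both groups need an ophthalmology clinic, so naming it says nothing about referral.
- **Women of unknown glucose status qualifying as controls.** The definition requires normal status, and unknown is not normal. The missing detail is which test established it and when.

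**Conclusion.** The point holds as a gap in the control definition and in the timing of measurement. As written, the plan fixes weeks of pregnancy only for the cases' diagnosis, dates the eye and tear measurements in neither group, and, in the SAP text available, compares the groups without adjustment. A stage difference can therefore enter every eye and tear comparison.

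Whether it does, how far and in which direction cannot be told from the documents. The illustrations run from nearly harmless (0.05 SD) to more than double the nominal error rate (0.20 SD). They rest on assumed shifts, equal SDs and a two-sided 5% level. The finding does not extend to selection through the eye clinic or to controls whose glucose status was never assessed.

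This goes beyond a request for missing detail, because a common window is a specific, inexpensive change that would reduce the bias if there is any. It should be made; confidence that it alters the results is low.

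**What to change.** **Definition.** Define controls as women with a normal result on the same 24-28 week glucose testing that yields the cases. Set one interval from that test to the OCT and tear strip, identical in both groups. State the recruitment source of each group.

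**Women already enrolled.** The Protocol describes the 60 women as having taken part, so the practical step is to retrieve test and examination dates from file. Base the main comparison on controls who meet the definition. Where the weeks of examination overlap but differ between groups, adjust for gestational age at examination. Report its distribution by group in any case.

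**Cost.** The work is a wording change, a check of dates and possibly one covariate. The real downside is losing controls. Six of 34 lost takes power at 0.742 SD from 80% to 76%; keeping only 24 gives 73%, and keeping 17 gives 64%. If losses are of that larger order, report the gestational-age-adjusted analysis of all 60 alongside the restricted comparison. If the dates show that controls already meet the definition and the groups were examined at similar weeks, only the wording changes.

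### Does the absence of a named primary outcome among the fundus, OCT and tear comparisons call for a change to the plan?

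*Protocol*

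**What the plan says.** The Protocol's title, "Fundus Finding and Thiol-Disulfide Homeostasis in Gestational Diabetes", sets an eye domain and an oxidative-stress domain side by side. The body does the same: "At the end of the study, fundus findings and tear oxidative stress values of both groups will be compared". Two of the eye measures are specific: "Optic nerve retinal nerve fiber thickness and macular thickness were measured with OCT device in all patients". The Protocol also lists a dilated fundus examination, whose results would count as fundus findings. On the tear side it says that "ELISA method will be used for determination of tear oxidative stress findings", without listing analytes. There are 26 women with impaired glucose status and 34 controls.

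The SAP (Statistical analysis) gives one rule for every quantitative outcome. After a Shapiro-Wilk check, "Mann-Whitney U test will be used in comparisons of two groups that do not show normal distribution of quantitative data", and Student's t test otherwise. Chi-square is used for qualitative data. For associations, "Pearson correlation analysis will be used in case of normal distribution and" Spearman's otherwise, and there the available text ends in mid-sentence. No significance level, ranking of outcomes, multiplicity rule or sample-size calculation appears in either document as supplied.

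**The concern.** With several between-group comparisons of equal standing and none named as the main one, a reader who later sees one nominally significant result cannot tell from these documents whether it was the intended question or the best of several. A primary outcome chosen after the results are known offers no protection against this.

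Timing seemed to add urgency. The Protocol reports enrolment as complete ("A total of 60 pregnant women participated in the study") and the OCT measurements as done, but puts the ELISA in the future. On that wording, a tear outcome is the only one that could still be named before its values exist. Two sentences in the SAP would do it, with no extra participants or measurements. At stake is how far a single positive finding from this study could be trusted.

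**Working it through.** **Inputs from the documents.** Group sizes are 26 and 34 (26 + 34 = 60, which agrees with the stated total). The quantitative outcomes that can be counted are nerve fibre thickness, macular thickness and at least one tear value, so at least three. The plan gives no error rate, power or detectable difference, so it has no figure of its own to reproduce.

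**Assumptions.** Two-sided 0.05 per test, no adjustment, all nulls true, any one significant result counted as a finding, and correlation between test statistics from 0 to 0.7. None of these is stated in the documents.

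**Step 1: three tests.** If independent, 1 − 0.95³ = 0.1426, or 14.3%. With a common correlation ρ, the chance is 1 − ∫φ(s)[Φ((1.96 − √ρ·s)/√(1 − ρ)) − Φ((−1.96 − √ρ·s)/√(1 − ρ))]³ds:

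| ρ | 0 | 0.3 | 0.5 | 0.7 | 0.9 | 1 |
|---|---|---|---|---|---|---|
| 3 tests | 14.3% | 13.6% | 12.5% | 10.9% | 8.4% | 5.0% |

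Simulated t tests with 26 and 34 women (40,000 studies per case) give 14.3%, 12.7% and 11.0% at ρ = 0, 0.5 and 0.7, so the normal approximation is adequate.

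**Step 2: other ways of counting.**
- Only the OCT pair correlated, at 0.7: the pair alone gives 8.35%, and with an independent tear value 1 − 0.95 × (1 − 0.0835) = 12.9%.
- Fundus domain as one comparison (two tests): 1 − 0.95² = 9.75%, or 8.35% at ρ = 0.7.
- Four, five or six independent comparisons: 1 − 0.95⁴ = 18.5%, 1 − 0.95⁵ = 22.6%, 1 − 0.95⁶ = 26.5%.

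The result therefore runs from 5% to above 26%, depending on a count and a correlation that the documents do not fix.

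**Step 3: what the plan's own rules give.** Each comparison, run by the SAP's rule, has its own error rate of 5% at the assumed level, however many others are run beside it. Familywise error rises only if one significant result among several is declared a success for the study, and no passage says that. Naming a primary would not alter any test or p-value. It would attach a label to one of them.

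**Step 4: sensitivity of a tear primary.** With 26 and 34 women, the noncentral t distribution gives 80% power at 0.742 SD. For Mann-Whitney with normal data, divide by √(3/π): 0.742/0.977 = 0.760 SD. Both assume that every woman gave a usable sample. The Protocol treats a Schirmer result of 15–20 mm as enough for assay, so some samples may fall short. If 10% failed (about 23 and 31 left), the figure is 0.79 SD. If 20% failed (about 21 and 27 left), it is 0.83 SD. The OCT measurements, by contrast, are reported for all women.

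**Step 5: the timing argument.** The Protocol is dated April 13, 2023, and cites ethics approval of 13.04.2023, the same day. Yet it describes 60 women as already enrolled and consented. With matching dates, the past tense may be a matter of drafting and is weak evidence of which data had been seen. The comparison of fundus findings is itself written in the future tense alongside the tear values. Having measured the OCT outcomes is also not the same as having compared them by group.

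**The case for a change.** The best case for acting is that the remedy is nearly free and the gap is real. No available sentence names a primary outcome, and the statement of planned comparisons sits in the Protocol, which is not cut off at that point. Three is a low count, because the tear results are described in the plural and the fundus examination adds more. Neither document calls the study exploratory. Whatever the correlation, a reader cannot separate a prespecified result from a selected one.

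Much of that stands. The designation is absent from the text available, the arithmetic is right under its assumptions, and a positive result from one of several unranked comparisons deserves caution. It does not show that anything the plan does specify would give a wrong answer. Nor can a concrete replacement be justified. The missing end of the SAP might already name a primary. If it named an OCT measure, installing a tear measure would itself switch the outcome, and declaring that none was prespecified would be untrue. The sentence that could be added would have to leave the analyte blank, because the documents do not list the analytes. Choosing the tear domain would also demote the domain the title lists first, on verb tense alone.

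**Conclusion.** No change to the plan follows. The gap is an unwritten label in a small observational comparison that makes no confirmatory claim, and the planned tests are valid at their own level as written. The 10.9% to 14.3% range holds only for three tests at an assumed 0.05, correlation between 0 and 0.7, all nulls true and an any-one-significant success rule. None of these is in the documents, and other plausible inputs move the figure either way. Promoting a tear outcome and barring an OCT outcome is at best a debatable trade-off. It depends on an uncertain reading of timing, and its 0.74 SD sensitivity assumes 60 usable tear samples (0.79 to 0.83 SD if 10% to 20% are lost, an assumed range). A sensible analyst would keep any primary outcome stated in the part of the SAP not available here and, failing that, report the comparisons as unranked, each at its own level. The judgement is confined to the text available, since the SAP is incomplete.
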